6.3. Six-Item Headache Impact Test

The HIT-6 was developed by [Kosinski et al \(2003\)](#) as a short form for reliably assessing the adverse headache impact in clinical practice and clinical research settings. The questionnaire measures the adverse impact of headache on social functioning, role functioning, vitality, cognitive functioning, and psychological distress. It also assesses headache severity. The HIT-6

has been shown to be a reliable and valid tool for assessment of headache impact in patients with CM (Yang et al 2011).

Patients with CM will complete the HIT-6 at time points specified in Table 1 (patients rolling over from the pivotal efficacy studies) and Table 2 (patients not rolling over from the pivotal efficacy studies).

6.4. Migraine Disability Assessment Questionnaire

The MIDAS questionnaire is a 5-item instrument developed to assess headache-related disability based on lost days of activity in 3 domains (work, household work, and nonwork) over the previous 3 months. The total of the scores of the first 5 questions is used for grading of disability, with scores of 0 to 5, 6 to 10, 11 to 20, and ≥ 21 interpreted as disability grades 1 (little or no disability), 2 (mild disability), 3 (moderate disability), and 4 (severe disability), respectively. It has been shown to be reliable and valid for migraine, with substantially higher scores in migraine cases than non-migraine cases (Stewart et al 1999a, Stewart et al 1999b).

Patients with EM will complete the MIDAS questionnaire at time points specified in Table 1 (patients rolling over from the pivotal efficacy studies) and Table 2 (patients not rolling over from the pivotal efficacy studies).

6.5. Two-Item Patient Health Questionnaire/9-Item Patient Health Questionnaire

The PHQ is a 9-item questionnaire with each item corresponding to 1 criterion of the Diagnostic and Statistical Manual for Mental Disorders 4th edition diagnostic criteria for major depressive disorder. Each of the items is scored on a scale of 0 (“not at all”), 1 (“several days”), 2 (“more than half the days”), and 3 (“nearly every day”) based on the frequency of symptoms during the past 2 weeks (Spitzer et al 1999). The PHQ-2 was developed from the PHQ-9 to rapidly screen for depression and consists of the first 2 questions from the PHQ-9. The PHQ-2 and the PHQ-9 are well-validated measures for detecting and monitoring depression, anxiety, and somatization (Kroenke et al 2010).

Patients will complete the PHQ-2 at time points specified in Table 1 (patients rolling over from the pivotal efficacy studies) and Table 2 (patients not rolling over from the pivotal efficacy studies). If the PHQ-2 is positive (ie, a score ≥ 3), patients will complete questions 3 through 9 [unique questions] of the PHQ-9.

6.6. Migraine-Specific Quality of Life Questionnaire

The MSQOL, version 2.1, is a 14-item questionnaire to assess the impact of migraine and migraine treatment on a patient’s quality of life during the previous 4 weeks, which has been shown to be a reliable and valid tool for use in CM and EM (Bagley et al 2012). The MSQOL measures the degree to which performance of normal activities is limited by migraine (Role Function-Restrictive domain comprising 7 items), the degree to which performance of normal activities is prevented by migraine (Role Function-Preventive domain comprising 4 items), and the emotional effects of migraine (Emotional Function domain comprising 3 items). Scores range from 0 to 100, with higher scores indicating better health-related quality of life.

Patients will complete the MSQOL at time points specified in [Table 1](#) (patients rolling over from the pivotal efficacy studies) and [Table 2](#) (patients not rolling over from the pivotal efficacy studies).

6.7. EuroQol-5 Dimension Questionnaire

The EQ-5D-5L is a standardized questionnaire that assesses overall state of health. The EQ-5D-5L consist of 2 parts. In Part 1, patients rate their health state in 5 domains: mobility, self-care, usual activities, pain/discomfort, and mood, using a scale of 1 to 5 where 1=no problems, 2=slight problems, 3=moderate problems, 4=severe problems, and 5=extreme problems. In Part 2, patients rate their health state on a 100 mm visual analog scale; a rating of 0 represents the worst imaginable health state, and a rating of 100 represents the best imaginable health state.

Patients will complete the EQ-5D-5L at the time points specified in [Table 1](#) (patients rolling over from the pivotal efficacy studies) and [Table 2](#) (patients not rolling over from the pivotal efficacy studies).

6.8. Patient Global Impression of Change Scale

The PGIC scale is a validated generic tool for assessment of overall change in the severity of illness following treatment. Patients will rate how they describe the change (if any) that their migraine/headaches have had in their general quality of life and health status since beginning the treatment in this study on a 7-point scale where 1=no change (or condition got worse); 2=almost the same, hardly any change at all; 3=a little better, but no noticeable change; 4=somewhat better, but the change has not made any real difference; 5=moderately better, and a slight but noticeable change; 6=better, and a definite improvement that has made a real and worthwhile difference; and 7=a great deal better, and a considerable improvement that has made all the difference.

Patients will complete the PGIC scale at time points specified in [Table 1](#) (patients rolling over from the pivotal efficacy studies) and [Table 2](#) (patients not rolling over from the pivotal efficacy studies).

6.9. Work Productivity and Activity Impairment Questionnaire

The generic version of the WPAI questionnaire measures the overall effect of health on productivity at work and daily activities. The specific health problems version of the WPAI questionnaire allows investigators to attribute productivity and activity impairment issues to specific health conditions. After the employment status of a respondent is identified, 3 open-ended questions are asked concerning (1) hours absent from work due to health problems (or specific condition), (2) hours absent from work due to other reasons, and (3) hours actually worked. Two additional questions are included that ask about the impact of health on productivity, 1 concerning productivity at work and the other concerning daily activities outside of work. The response format of each item of the WPAI questionnaire consists of an 11-point scale ranging from 0 (no impairment) to 10 (complete impairment) ([Reilly et al 1993](#)).

Patients will complete the WPAI questionnaire at time points specified in [Table 1](#) (patients rolling over from the pivotal efficacy studies) and [Table 2](#) (patients not rolling over from the pivotal efficacy studies).

7. ASSESSMENT OF SAFETY

In this study, safety will be assessed by qualified study personnel by evaluating the following: reported adverse events, clinical laboratory test results, vital signs measurements, 12-lead ECG findings, physical examination findings (including body weight measurements), eC-SSRS scores, local injection site assessments, and concomitant medication usage.

7.1. Adverse Events

7.1.1. Definition of an Adverse Event

An adverse event is any untoward medical occurrence in a patient administered a pharmaceutical product, regardless of whether it has a causal relationship with this treatment.

In this study, any adverse event occurring after the clinical study patient has signed the informed consent form for this study should be recorded and reported as an adverse event.

An adverse event can, therefore, be any unfavorable and unintended physical sign, symptom, or laboratory parameter that develops or worsens in severity during the course of this study, or significant worsening of the disease under study or of any concurrent disease, whether or not considered related to the study drug. A new condition or the worsening of a pre-existing condition will be considered an adverse event. Stable chronic conditions (such as arthritis) that are present before study entry and do not worsen during this study will not be considered adverse events.

Accordingly, an adverse event can include any of the following:

- intercurrent illnesses
- physical injuries
- events possibly related to concomitant medication
- significant worsening (change in nature, severity, or frequency) of the disease under study or other pre-existing conditions (Note: A condition recorded as pre-existing that is intermittently symptomatic [eg, headache] and that occurs during this study should be recorded as an adverse event.)
- drug interactions
- events occurring during diagnostic procedures or during any follow-up period of this study
- laboratory or diagnostic test abnormalities that result in the withdrawal of the patient from the study, are associated with clinical signs and symptoms or a serious adverse event, or require medical treatment or further diagnostic work-up, or are considered by the investigator to be clinically significant (Note: Abnormal laboratory test results at the screening visit that preclude a patient from entering the study or receiving study drug are not considered adverse events.)
- all events of possible drug-induced liver injury with hyperbilirubinemia (defined as AST or ALT $\geq 3 \times$ the ULN, plus either total bilirubin $\geq 2 \times$ the ULN or INR > 1.5) or

Hy's Law events require immediate study treatment cessation and reporting as a serious adverse event. Refer to [Appendix E](#) for guidance regarding monitoring patients with elevated liver function tests.

Migraine exacerbations, including acute headache, requiring headache medications will be collected as part of the efficacy assessment in this study. Migraine exacerbations (including acute headache) should be recorded as an adverse event only if the presentation and/or outcome is more severe than would typically be expected from the normal course of the disease in a particular patient or if they are severe enough to require hospitalization of the patient, in which case they are recorded as serious adverse events.

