- to evaluate the efficacy of sc TEV-48125 in patients with migraine, as assessed by the reduction in the number of migraine days in patients not receiving concomitant migraine preventive medications at baseline
- to evaluate the efficacy of sc TEV-48125 in patients with migraine, as assessed by the reduction in the number of headache days of at least moderate severity in patients not receiving concomitant migraine preventive medications at baseline
- to evaluate the efficacy of sc TEV-48125 in patients with migraine, as assessed by the reduction in the number of migraine days for new patients and placebo-treated rollover patients
- to evaluate the efficacy of sc TEV-48125 in patients with migraine, as assessed by the reduction in the number of headache days of at least moderate severity for new patients and placebo-treated rollover patients
- to evaluate the efficacy of sc TEV-48125 in patients with migraine, as assessed by the reduction of the number of headache days of any severity
- to evaluate the efficacy of sc TEV-48125 in patients with migraine, as assessed by the reduction of the use of any acute headache medications
- to evaluate the efficacy of sc TEV-48125 in patients with migraine, as assessed by the discontinuation of use of concomitant preventive medications
- to evaluate the efficacy of sc TEV-48125 in patients with migraine, as assessed by the reduction of migraine-related disability and change in quality of life
- to evaluate the immunogenicity of TEV-48125 and the impact of ADAs on clinical outcome in patients exposed to sc TEV-48125
- to explore the correlation between pharmacokinetic parameters and drug efficacy
- to explore the relationship between genetic polymorphisms within the CGRP receptor-ligand complex (eg, CALCA, CALCB, CALCRL, CRCP, and RAMP) and migraine-associated genes (eg, PRDM16, AJAP1, TSPAN2, MEF2D, TRPM8, TGFB2, PHACTR1, FHL5, C7orf10, MMP16, ASTN2, LRP1, APOA1BP, TBC1D7, FUT9, STAT6, ATP5B, and MTHFR) and mode-of-action-related pathways versus hypertension, migraine severity, and safety and efficacy responses

- to explore the relationship between biofluid bone, angiogenic, and inflammatory biomarkers with TEV-48125 concentrations and efficacy responses

Study Endpoints:

Primary Endpoints: The safety and tolerability endpoints for this study are as follows:

- occurrence of adverse events throughout the study

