1.4.1.1. Risks of TEV-48125

Identified risks (adverse drug reactions) of TEV-48125 include injection site erythema, administration site pain, injection site pain, injection site pruritus, injection site dermatitis, infusion-related reaction, and drug hypersensitivity. None of the identified risks are considered important risks.

Potential risks for TEV-48125 are perivascular inflammation; development of antidrug antibodies (ADAs); liver enzyme elevations; and cardiovascular consequences of CGRP inhibition, including effects on blood pressure, heart rate, or other cardiovascular parameters.

As described in Section 1.3.2.2, sc TEV-48125 has generally been well tolerated over the ranges of doses evaluated (single doses of 0.02 to 2000 mg in healthy volunteers, multiple doses of 30 to 300 mg in healthy volunteers, and multiple doses of 225 to 900 mg in migraine patients). The most common treatment-emergent adverse events across the clinical program were mild to moderate transient general administration site disorders/reactions. Other commonly reported treatment-emergent adverse events were headache, back pain, and upper respiratory tract infection.

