First treatment administration (ie, for this study) will occur at visit 2, and additional doses will be administered at each visit (approximately every 4 weeks) through visit 13. Patients will return for the EOT visit (visit 14) approximately 4 weeks after administration of the final dose of study drug, and they will return approximately 7.5 months (225 days [the approximate equivalent of 5 half-lives]) after administration of the final dose of the study drug for collection of adverse event and concomitant medication information and samples for pharmacokinetic, immunogenicity, and biomarker analyses.

Headache information will be captured using an electronic headache diary device as follows:

- For patients rolling over from the pivotal efficacy studies, headache information will be captured daily during the first 3 months, during the 4-week period after visit 7, and during the 4-week period after visit 13.

- For patients not rolling over from the pivotal efficacy studies, headache information will be captured daily during the first 4 months, during the 4-week period after visit 7, and during the 4-week period after visit 13.

Assessments of migraine-related disability and change in quality of life (using the HIT-6 or MIDAS questionnaire, PHQ-2/PHQ-9, PGIC scale, MSQOL questionnaire, EQ-5D-5L questionnaire, and WPAI questionnaire), safety evaluations, and collection of pharmacokinetic, immunogenicity, and biomarker samples will be performed throughout the study according to the schedules of assessments ([Table 1](#), [Table 2](#), and [Table 3](#)) and [Section 3.14](#).

[figure not shown]
Patients who withdraw from the study before completing the 12-month treatment period will have EOT visit (visit 14) procedures and assessments performed at their final visit, and they will be asked to return for the follow-up visit approximately 7.5 months (225 days [the approximate equivalent of 5 half-lives]) after their last dose of study drug.

The study schemas for patients with CM and EM who receive study drug in the current study are presented in [Figure 1](#) and [Figure 2](#), respectively.

The end of the study is defined as the date the last patient attends the follow-up visit (visit 15).

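### Protocol Section 7.1.1 gives two inconsistent rules for recording headache as an adverse event and does not say which governs, so headache, migraine and any-AE incidence may depend on site practice.

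*Protocol*

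**What the plan says.** All the relevant recording text is in Protocol Section 7.1.1.

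- A general sentence says that stable chronic conditions "present before study entry and do not worsen during this study will not be considered adverse events"; its example is arthritis.
- A bullet lists as an AE "significant worsening (change in nature, severity, or frequency) of the disease under study or other pre-existing conditions".
- A parenthetical note to that bullet says that a pre-existing condition that is "intermittently symptomatic [eg, headache] and that occurs during this study should be recorded as an adverse event".
- The closing paragraph covers the study disease: "Migraine exacerbations, including acute headache, requiring headache medications will be collected as part of the efficacy assessment in this study". Such an exacerbation "should be recorded as an adverse event only if the presentation and/or outcome is more severe than would typically be expected" in that patient, or if it is bad enough to need hospitalisation, in which case it is a serious AE.

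The endpoint concerned is "occurrence of adverse events throughout the study", the first of seven safety endpoints that the synopsis lists as primary. SAP Section 7.3 counts each patient once per preferred term or system organ class and says nothing specific about headache or migraine terms.

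**The concern.** The note is triggered when the condition occurs; the closing paragraph is triggered only when an episode is worse than that patient's usual course. Headache is both the note's example and the symptom that brings patients into the study, so the two rules meet on the same events.

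The study is descriptive (Protocol Section 9.6 rules out inferential analysis), and Protocol Section 3.9 calls it uncontrolled. The reported incidence is therefore itself the result, with no concurrent placebo group against which a recording habit would cancel. Because a patient counts once per term, a single routine headache entered as an AE is enough to make that patient a case for headache and for any AE.

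**Working it through.** No figure in the plan depends on this point, so there is nothing to reproduce. The check is to apply each rule to the same events.

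| Headache during the study | Note, read literally | Bullet, worsening only | Closing paragraph |
|---|---|---|---|
| Usual severity and frequency | AE | Not an AE | Not an AE |
| Usual severity, significantly more frequent | AE | AE | Apparently not an AE |
| Worse than usual for that patient | AE | AE if significant | AE |
| Needs hospitalisation | AE | AE | Serious AE |

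The rules broadly agree in the last two rows. They disagree in the first row if the note is read literally. They disagree in the second row even if the note is read down to its parent bullet, because the bullet names frequency and the closing paragraph turns on severity.

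**Does the context settle it?** Three things favour the closing paragraph: the note hangs from a bullet about significant worsening, stable conditions are excluded, and the closing paragraph is the only disease-specific rule. Two things leave room for the literal reading. If the note required worsening, it would only repeat its bullet. The section also uses arthritis as its example of a stable condition and headache as its example of an intermittent one, which a site could take as two classes with two rules. No sentence states precedence.

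**Is ordinary headache captured elsewhere?** Only in part. For rollover patients the diary is "captured daily during the first 3 months, during the 4-week period after visit 7, and during the 4-week period after visit 13"; SAP Section 4.5 derives months 1, 2, 3, 6 and 12 for everyone. That is 5 of 12 four-week periods, or 5 × 28 = 140 of 12 × 28 = 336 treatment days, and none of the 533 − 336 = 197 days from end of treatment to the final visit. Outside those windows the closing paragraph's reliance on efficacy collection has no diary behind it.

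**Illustration of the literal reading.** Inputs: new-patient entry criteria in Protocol Section 4.1.2 (4 to 14 headache days per 28 for episodic migraine, at least 15 for chronic) and 12 treatment periods. Assumptions not in the documents: a constant proportional reduction r, and Poisson counts.

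- Expected headache days = baseline days × 12 × (1 − r).
- r = 0: 4 × 12 = 48; 14 × 12 = 168; 15 × 12 = 180.
- r = 0.75: 12, 42 and 45.
- Chance of no headache day = exp(−expected days). At the episodic minimum: exp(−12) ≈ 0.000006 with r = 0.75; with r = 0.90, 4 × 12 × 0.10 = 4.8 and exp(−4.8) ≈ 0.008.

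A site that followed the note literally would therefore record at least one headache AE for nearly every patient. The documents give no rate for unusually severe episodes, so the gap between the two rules cannot be calculated.

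**The case against.** The strongest reply is that the section, read as a whole, already answers the question. The note is a parenthesis to a worsening bullet, stable disease is excluded, and a specific closing rule ordinarily governs a general illustrative note. Protocol Section 7.1.2 points the same way: sites ask about unusual symptoms and record manifestations of a disease under one diagnosis. Most of this stands, and many sites may well follow the closing paragraph. It does not settle the matter, because the precedence is inferred rather than written and the frequency conflict remains on the narrower reading. Section 7.1.2 also requires AEs to be recorded whatever their severity.

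A reader might infer more than the documents support:

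- **That every recurrence must be entered as an AE.** The note speaks of recording a condition, not of one AE per episode, and its parent bullet limits it.
- **That the primary endpoint is undefined.** AEs are defined in general, the closing paragraph is a usable rule, and AE occurrence is one of seven safety endpoints.
- **That headache is the commonest AE.** Protocol Section 1.4.1.1 says otherwise: "The most common treatment-emergent adverse events across the clinical program were mild to moderate transient general administration site disorders/reactions". Headache is listed among other common events.
- **That the headache-day counts measure the harm.** They come from criteria for new patients, about 300 of 1842 planned, and the largest assume no treatment effect. The AE analysis counts patients, not days.

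The consequence is also bounded. No test, power or error rate is affected. Sites are blinded, so the ambiguity is not tied to regimen. Hospitalised exacerbations remain serious AEs.

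**Conclusion.** The inconsistency is real and more than clerical. Section 7.1.1 contains a stated rule which, if followed literally, would push headache and any-AE incidence towards 100%, beside a rule that admits only unusually severe episodes. The context favours the second, but neither document says so and the SAP does not correct it at analysis. The supported conclusion is that recording of headache and migraine terms, and hence their incidence and any-AE incidence, may differ between sites. The size is unknown: it depends on how many sites follow the note, which the documents do not show, and on the rate of unusually severe episodes, which they do not give. It should be corrected, but it does not undermine the safety objective as a whole.

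**What to change.** In Protocol Section 7.1.1:

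- remove headache as the note's example, or limit the note to worsening;
- state which rule governs migraine and headache;
- state whether a change in frequency alone, at usual severity, is an AE.

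Send sites the same text as a clarification. The cost is a sentence or two and a letter; the sponsor has already used administrative letters for clarifications (Protocol Sections 17.2 and 17.3).

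If data have already been collected under the present wording, add to SAP Section 7.3 a presentation of any-AE incidence with and without headache and migraine preferred terms, with the terms listed before the tables are produced. This needs no new data and shows how far the reported incidence depends on those terms.
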